However, food pantries are not a long-term solution to improve health for food insecure people with T2D. Most food pantries do not provide food of sufficient dietary quality to support a healthy lifestyle, particularly for vitamins A and C and calcium.²² Current food pantry clients' diet quality is insufficient for caloric intake, fruits, vegetables, and dairy.²³

Diabetes self-management education (DSME) is an approach with documented efficacy in helping people manage T2D. DSME supports informed decision-making, encourages goal setting and problem solving, and improves self-care behaviors.²⁴ Across many populations, DSME improves glycemic control,²⁵ lowers body mass index (BMI),²⁶ improves diabetes knowledge,²⁷ diet quality,²⁸ physical activity,²⁹ and self-efficacy;²⁷ reduces health care costs and hospitalizations,^{30,31} and increases use of primary care and preventive services.³²

Recent studies have shown promise for DSME among food pantry clients with T2D. One study paired DSME classes with T2D-appropriate food boxes distributed at food banks and found significant improvements in glycemic control.³³ However, this study suffered from problems with attendance and retention, retaining only 42% of participants. In a follow-up trial, only 20% engaged fully with the DSME and food box intervention (i.e., picked up ≥ 9 of 11 food distributions, attended 2 DSME classes, etc.).³⁴

By removing barriers to attendance and retention, our research team will leverage the full potential of home-delivered T2D-appropriate food boxes paired with DSME. We have

Title: Delivering Health: An Integrated Approach to Address Diabetes in the Context of Food Insecurity

PI: [name]

successfully adapted diabetes education for delivery in community settings, including homes, faith-based organizations, and community centers.³⁵ We have adapted DSME for people from diverse cultural backgrounds who face economic, transportation, health care, and health literacy barriers.³⁶ We are experienced at developing interventions to improve health of low-income food insecure people, including food pantry interventions to improve access to healthy food.^{37,38}

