The 12 adapted modules are presented in **Table 1**. In the study, these modules will be delivered to the participants on paper in the T2D-appropriate food boxes and in easy to access online versions, which link to the videos summarizing the key concepts and demonstrating cooking techniques. All materials are translated into English, Spanish, and Marshallese.

2. Design T2D-appropriate food boxes. The project team led by an endocrinologist, registered nurse, and registered dietitian designed 12 weekly food boxes to be home delivered to each participant. The boxes were adapted from the American Diabetes Association Create Your Plate method,⁴⁹ which emphasizes non-starchy vegetables, proteins, and grains, consistent with the meal pattern promoted in the ACP DSME.⁴⁸ In addition, the boxes will include food that largely reflects Feeding America's Foods to Encourage framework,⁵⁰ which was developed by nutrition experts and food bank leaders to meet USDA dietary guidelines⁵¹ and MyPlate framework.⁵²

The boxes will include ~9,000 calories of food, equivalent to the amount the average household would receive *pro-rated per week* from an average Arkansas food pantry.³⁷ Each box will include fresh fruits and vegetables, as well as the ingredients necessary to prepare the recipes included with that week's DSME curriculum. If a certain item is unavailable or out of stock, there is a list of potential substitutions that are of equal nutritional content compared to the first choice food item. Each week's box will include an educational fact sheet of the week's DSME module, including links and QR codes leading to the videos. Links to the week's online materials, which present the same content as the paper materials, will be texted or emailed to each participant based on their preferred contact method on the day each box is delivered. **Table 2** shows an example T2D-appropriate food box.

3. Recruit and enroll up to 110 participants. Study participants may be

recruited from waiting areas of food pantries located in Benton and Washington Counties in northwest Arkansas. (See Letters of Support from local food pantries.) Due to social distancing and public health guidelines related to COVID-19 each of the food pantries have established drive-thru clinics where participants can remain isolated in their vehicles while completing data collection. Participants may use these drive-thru clinics for consent and all biometric collection.

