The study has a single-arm, pre-post study design. All participants will receive the intervention (i.e., 12 weekly food boxes including the adapted DSME materials). Our target sample size for recruitment is 100. Assuming a repeated measures t-test, two-sided $\alpha=.05$, and a Pearson correlation between repeated measures of $r=.5$, we will have 80% power to detect a Cohen's d effect size of 0.28. For context, Chrvala, Sherr, & Lipman's (2016) meta-analysis found that on average DSME led to a 0.6% improvement in HbA1c.²⁵ Assuming a standard deviation of 1.5%, this translates to Cohen's d of 0.4 (i.e., $0.6/1.5=0.4$). Thus, the proposed intervention with a sample size of 100 is powered to detect a small-to-medium effect consistent with the expected effect size for standard DSME interventions in the context of research trials, and smaller than the effect found in previous food pantry-based DSME interventions.^{33,34}

Table 3. Delivering Health study measures and outcomes	
Variables	Instrument(s) or Measure(s)
COVARIATES	
Demographic & Socioeconomic	Demographic (age, gender, marital status, race, number of adults and children in the household) and socioeconomic (education, employment status, insurance coverage, WIC and SNAP benefits) variables will be captured using validated questions from the Behavior Risk Factor Surveillance System (BRFSS) ⁶² and National Health Interview Study (NHIS). ¹²⁰
EFFECTIVENESS OUTCOMES	
HbA1c	Finger stick blood collection will be used to test HbA1c using a Siemens DCA Vantage analyzer that can be taken into the field. ⁶³
Diet Quality and Fruit and Vegetable Consumption	Skin carotenoid level will be measured using a Veggie Meter® optical skin scanner, which uses Raman Spectroscopy. The Veggie Meter assesses frequency changes in reflected light to calculate carotenoid presence. 24-hour dietary recalls will be collected using the widely-used Nutrition Data System for Research (NDSR) software, which includes over 18,000 foods. ⁶⁴ NDSR will be used to calculate Healthy Eating Index-2015 (HEI) scores and fruit and vegetable consumption. HEI-2015 scores comprise nine

Title: Delivering Health: An Integrated Approach to Address Diabetes in the Context of Food Insecurity

PI: [name]

	component scores (e.g., vegetables, dairy) and are recommended by National Cancer Institute to assess impact of diet quality interventions. ^{65,66}

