Table 4. DSME and T2D-appropriate Food Boxes Intervention

Evidence-based DSME Curriculum	■ Consistent with the American Association of Diabetes Educators, the adapted ACP DSME will cover the topics of understanding diabetes, eating right, being active, checking blood sugar, taking medicines, keeping feet healthy, and insulin. The adapted curriculum consists of 12 modules, which will include recipes and information on cooking and shopping when on a limited income and with foods commonly found at food pantries.
T2D-appropriate food boxes	■ Each weekly food box will include ~9,000 calories of food, equivalent to the amount the average household receives prorated per week from an average Arkansas food pantry. ³⁷ The boxes will follow the American Diabetes Association Create Your Plate method, consistent with the ACP DSME. Food will be purchased from a local grocery store.
Intervention Delivery	■ Food boxes will be delivered to participants' homes once per week. Each week's box will include a two-page educational fact sheet version of the week's DSME module, including links and QR codes leading to videos supporting the week's curriculum module. Links to the week's online materials, which present the same content as the paper materials, will be texted or emailed to each participant the day their box is delivered.
Dosage	■ 12 food boxes (including curriculum) delivered once per week over 12 weeks

Given the study's longitudinal design, participant retention will be crucial. We engaged stakeholders to develop a retention plan. The plan specifies that study staff responsible for recruitment and retention will be bilingual (Spanish/English or Marshallese/English). Study staff will obtain each participant's contact information and preferred method of contact. Before each follow-up data collection visit or call, research staff will contact participants about the upcoming data collection.

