To examine the intervention's effect on the primary outcomes of glycemic control as measured by HbA1c and diet quality as measured by Healthy Eating Index-2015 (HEI) scores, we will use mixed effects regression models for repeated measures. These analyses will focus on testing for a statistically significant difference between pre-intervention versus post-intervention measures. Additional analyses will include relevant covariates such as sex or age. We will also explore models that include process indicators of dosage of intervention received (e.g., number of food boxes received) to examine whether dosage predicts change in primary outcomes.

Ethical Considerations

This study will be conducted in accordance with all applicable government regulations and University of Arkansas for Medical Sciences research policies and procedures. This protocol and any amendments will be submitted and approved by the UAMS Institutional Review Board (IRB) to conduct the study.

The formal consent of each subject, using the IRB-approved consent form, will be obtained before that subject is submitted to any study procedure. All subjects for this study will be provided a consent form describing this study and providing sufficient information in language suitable for subjects to make an informed decision about their participation in this study. The person obtaining consent will thoroughly explain each element of the document and outline the risks and benefits, alternate treatment(s), and requirements of the study. The consent process will take place in a quiet and private room, and subjects may take as much time as needed to make a decision about their participation. Participation privacy will be maintained and questions regarding participation will be answered. No coercion or undue influence will be used in the consent process. This consent form must be signed by the subject and the person obtaining the consent. A copy of the consent will be given to the participant, and the informed consent process will be documented in the research record.

A \$40 Walmart gift card will be provided to the participant each time they complete a data collection event. If they complete both data collection events, they will receive a total of \$80 in Walmart gift cards.

Dissemination of Data

Title: Delivering Health: An Integrated Approach to Address Diabetes in the Context of Food Insecurity

PI: [name]

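### Does the exploratory model of food boxes received need a stated power and a rule for reading a null result?

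*Combined protocol and SAP*

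**What the plan says.** After describing mixed models for the two primary outcomes, HbA1c and the HEI-2015 score, the Data Analysis section adds that the team will explore models with "process indicators of dosage of intervention received (e.g., number of food boxes received) to examine whether dosage predicts change in primary outcomes". Table 3 lists boxes successfully received among the process indicators. Table 4 sets the dosage at "12 food boxes (including curriculum) delivered once per week over 12 weeks", so the count runs from 0 to 12.

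The sample-size paragraph (Study Design and Procedures, item 4) deals only with the mean pre-post change. It states "Our target sample size for recruitment is 100", a two-sided 5% level, a pre-post correlation of 0.5, and 80% power for d = 0.28. For context it cites a meta-analysis that "found that on average DSME led to a 0.6% improvement in HbA1c". It then continues "Assuming a standard deviation of 1.5" percentage points, which gives d = 0.4. Enrolment may reach 110.

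The documents do not give the expected spread of boxes received, a detectable slope, or a reading rule for a null dose result.

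**The concern.** With no control group, a dose-response pattern is one of the few internal clues that the boxes, rather than time or regression to the mean, moved HbA1c. A report that HbA1c fell but dosage did not predict the fall could be read as evidence against the boxes. If the slope is poorly estimated, that report is likely even when the boxes caused the whole change.

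Suppose each box contributes 0.05 points and all 100 participants are analysed. In simulation, the chance of a significant mean fall together with a non-significant slope was 46% when receipt was uniform on 1 to 12, 76% when uniform on 6 to 12, and 90% when mostly 10 to 12.

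A box count also records deliveries rather than what the participant ate, since "The boxes will include ~9,000 calories of food, equivalent to the amount the average household would receive" in a prorated week. That limits interpretation, but it does not by itself pull the slope towards zero.

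**Working it through.** **1. The plan's own figure.** With r = 0.5, the standardised change is d/√(2(1 − r)) = 0.28/√1 = 0.28. The noncentrality is 0.28 × √100 = 2.8 on 99 df, so power is 79.2% (normal approximation 80.0%). The stated 80% reproduces. At d = 0.4 the power is 97.7%. Both figures concern the mean change, not the slope.

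**2. Power for the box slope.** With two time points and complete data, a dose-by-time term amounts to regressing change on boxes.

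- SD of change = 1.5 × √(2(1 − 0.5)) = 1.5.
- If 0.6 points is the full 12-box effect and is linear in boxes (both assumptions), the slope is 0.6/12 = 0.05 per box.
- SE = 1.5/(SD of boxes × √100).
- Noncentrality = 0.05 × SD of boxes × 10/1.5 = SD of boxes/3, on 98 df.
- The 95% half-width over 12 boxes is 12 × 1.984 × SE.

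The receipt patterns below are assumed. The last column takes three favourable choices together: 110 analysed, baseline adjustment (residual SD 1.5 × √(1 − 0.25) = 1.30), and 0.6 as the cohort-average change (slope 0.6/mean boxes).

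| Boxes received | Mean | SD | Power at 0.05 per box, N = 100 | Half-width over 12 boxes (HbA1c points) | Power, all favourable choices |
|---|---|---|---|---|---|
| Half 0, half 12 | 6 | 6.00 | 51% | 0.60 | over 99% |
| 20% at 0, 80% at 12 | 9.6 | 4.80 | 35% | 0.74 | 67% |
| Uniform 1–12 | 6.5 | 3.45 | 21% | 1.03 | 72% |
| Uniform 6–12 | 9 | 2.00 | 10% | 1.79 | 19% |
| 12 − Binomial(4, 0.25) | 11 | 0.87 | 6% | 4.12 | 7% |

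As an example of the last column, uniform 6–12 gives a slope of 0.6/9 = 0.0667 and a noncentrality of 0.0667 × 2 × √110/1.30 = 1.08, hence 19%.

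**3. Is 51% a ceiling?** An SD of 6 is the largest a 0–12 count can have, so it is tempting to treat 51% as a cap. It is not one. At the same half-and-half split:

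- 110 analysed: 55%.
- Baseline adjustment, N = 100: 63%; with 110: 67%.
- 0.6 as the cohort average, which is how the sample-size paragraph uses it: slope 0.6/6 = 0.10, noncentrality 4, power 98%.
- In the other direction, on the step 2 assumptions, 80 completers give 42% and 42 completers give 24%.

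**4. Which receipt pattern applies?** The documents do not say. Home delivery is meant to remove attendance barriers, and follow-up comes one week after the twelfth delivery, so high receipt among those with follow-up data is a reasonable inference but not a stated fact. The Background's report that "only 20% engaged fully with the DSME and food box intervention" is little guide here, since that trial counted pick-ups and class attendance.

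**5. HEI-2015.** The documents give neither an expected effect nor an SD, so no figure can be computed.

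**The case for a change.** The strongest case for changing the plan is that in the high-receipt patterns a null slope is uninformative under every reading tried, at or below about 19% for uniform 6–12 and about 7% for mostly 10–12. The better the delivery works, the less this analysis can show. Results will be published and returned to participants, and two or three sentences would guard against misreading at no cost in data.

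The statistical part of this stands: with near-complete receipt, a non-significant slope says almost nothing about whether boxes matter. What does not follow is that the plan is wrong. It says the team will explore these models, claims no power for them, and draws no inference from a null. Asking whether dosage predicts change already implies a dose-by-time term. Reporting the slope with its interval and calling it an association is ordinary practice for an exploratory model. With half-widths of 1.79 or 4.12 points against an expected 0.6, the interval itself would show that the result is inconclusive. The feared misreading lies in a future report, not in anything the plan commits to.

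**Conclusion.** The concern does not call for a change. The plan leaves out detail on a secondary, exploratory line, and analysts fill that gap sensibly.

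For HbA1c, power is about 51% at the half-0, half-12 split if 0.6 points is the full 12-box effect, linear in boxes, and analysed as unadjusted change in 100 completers. On the same assumptions it is about 6% to 35% where most boxes are received. Relaxing those assumptions within what the plan allows raises the half-and-half figure to between 55% and over 99%. It still leaves at most about 19% for uniform 6–12 receipt and about 7% for mostly 10–12.

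A null slope should therefore be read as inconclusive if receipt proves high. How much this matters depends on a receipt distribution that the documents do not give. The primary pre-post tests, their sample size and their stated power do not depend on it.
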